Statistical Analysis for Phase II/Aim 2. Sixty patients (N=60) will be randomized into two equal sized groups with 1:1 ratio, either to TOLF or e-Lymph group. *Feasibility* will be assessed by examining (a) study accrual of breast cancer patients (N=60 over 9 months), (b) protocol adherence (>80% adherence to the protocol [defined in this study as the degree to which participants are willing and able to complete the intervention exposure], e.g., TOLF or e-Lymph), and (c) participant retention (>80% data collected at the study appointments). *Acceptability* will be assessed post-intervention using the validated scale of patient satisfaction and acceptability and exit interview.⁷⁷ *Evidence of Promising Outcomes.* Assuming a minimum protocol adherence of 80%, there will be at least 48 participants who will rate whether treatment is acceptable. Assuming acceptability is 50% which has the most conservative precision interval, the acceptability will be estimated within 8%.

Primary Endpoint. The primary endpoint is the complete reduction of lymphatic pain and reduced pain severity and interference reported by participants, and reduced lymph fluid level at week 13 post intervention.

Statistical Analysis for Outcomes. We hypothesize that participants who receive the TOLF will have better primary and secondary outcomes than participants who receive the control e-Lymph over time. Since outcomes will be measured at week 0 (baseline), 9 weeks and 13 weeks post intervention, generalized estimating equation (GEE) model will be used for analyzing each outcome to accommodate the correlation among the repeated measurements within a same subject.⁷⁸ Different working correlation matrices will be tested to select the most appropriate one for the GEE models. Identity link and logit link will be used for continuous outcomes (lymphatic pain severity, pain severity and interference, lymph fluid level, daily living

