function, psychological distress, QOL, and self-efficacy for pain management) and binary outcome (complete pain reduction), respectively. The predictors include two indicators of intervention and control groups respectively. Covariates found to be significantly different between the groups at baseline, will be included in the GEE model.⁷⁹ If the primary outcomes of the intervention group are significant at alpha 0.05, we will conclude the intervention works better than the control. Proper methods will be used to address any missing data to maximize the statistical power of our analyses and reduces the likelihood of systematic bias in estimates.

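### The rule for concluding that TOLF works better than e-Lymph is worded as a test of the TOLF arm and names no between-arm contrast, so it does not match the comparative hypothesis

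*Combined protocol and SAP*

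**What the plan says.** Everything relevant is in section 1.9.b (Data Analysis and Interpretations), under the Phase II statistical analysis.

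- **Hypothesis.** It is comparative and directional: "participants who receive the TOLF will have better primary and secondary outcomes than participants who receive the control e-Lymph over time".
- **Endpoint.** It is set at week 13 and worded as reductions, with no mention of the control arm: "The primary endpoint is the complete reduction of lymphatic pain and reduced pain severity and interference reported by participants", followed by lymph fluid level.
- **Model.** A "generalized estimating equation (GEE) model will be used for analyzing each outcome to accommodate the correlation among the repeated measurements", with visits at weeks 0, 9 and 13. The link is identity for continuous outcomes and logit for complete pain reduction.
- **Predictors.** "The predictors include two indicators of intervention and control groups respectively". Baseline covariates that differ between groups may be added. No reference arm, visit term, arm-by-visit term or contrast is listed.
- **Decision rule.** "If the primary outcomes of the intervention group are significant at alpha 0.05, we will conclude the intervention works better than the control". Sidedness is not stated.
- **Size.** "Sixty patients (N=60) will be randomized into two equal sized groups with 1:1 ratio", so 30 per arm.

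**The concern.** The premise of the rule concerns one arm and its conclusion concerns two. An analyst who follows it literally could report a significant improvement within TOLF as superiority over e-Lymph and still be within the protocol.

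That matters because improvement common to both arms is realistic here. Section 1.7 enrols only women who report pain, including intermittent pain, which invites regression to the mean. Table 1 gives the e-Lymph arm four contact sessions, so attention effects are possible. Section 1.4 reports that 22% of controls in the earlier randomised trial reached complete pain reduction. The control arm is there to remove such shared improvement from the comparison, and a within-arm test leaves it in.

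**Working it through.** The plan gives no power or error figure for the outcome comparison, so there is none to reproduce. The check asks how often the rule would declare TOLF better when the two arms truly do equally well.

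**Inputs**
- From section 1.9.b: n = 30 per arm; alpha 0.05; retention target above 80%, so 0.8 × 30 = 24 per arm at the limit.
- From section 1.4: 22% complete pain reduction among controls in the earlier trial.
- From section 1.7: every woman has pain at entry, so complete reduction is 0% at baseline.
- Assumed: two-sided testing; a common true improvement of 0.3, 0.5 or 0.8 SD of change in both arms.

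**What the predictors sentence can mean**
1. *No intercept, one coefficient per arm.* The TOLF coefficient is that arm's own level, tested against zero (against a 50% rate under the logit link). This is not a comparison.
2. *Change from baseline within TOLF.* This is a within-arm test.
3. *Intercept plus two indicators.* The columns are redundant, but the TOLF minus e-Lymph difference is still estimable. If the e-Lymph column is dropped as reference, the TOLF coefficient is the between-arm difference.

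The text does not choose among these.

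**Continuous outcome, within-arm reading (2)**

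The chance of significance in the improving direction is P(T > t), where t is the 97.5% point on n − 1 degrees of freedom and T is noncentral t with noncentrality d√n. The critical value is 2.045 for n = 30 and 2.069 for n = 24.

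| Common improvement d | d√30 | n = 30 | d√24 | n = 24 |
|---|---|---|---|---|
| 0.3 | 1.643 | 36% | 1.470 | 29% |
| 0.5 | 2.739 | 75% | 2.449 | 65% |
| 0.8 | 4.382 | 99% | 3.919 | 96% |

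A GEE simulation (1000 trials per scenario, 30 per arm, three visits, correlation 0.5) agrees. The within-TOLF change at week 13 is significant in 38%, 77% and 98.5%.

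**Complete pain reduction, within-arm reading**

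Against a 0% baseline, the exact McNemar test needs 6 responders: 2 × 0.5⁶ = 0.031, whereas 5 responders give 2 × 0.5⁵ = 0.0625. With a true rate of 22% in both arms, P(X ≥ 6) is 67% for n = 30 and 44% for n = 24.

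**Between-arm contrast, same equal-arms truth**
- Binary outcome at 22% in both arms (exact enumeration of the pooled two-proportion z test): a favourable false conclusion in 2.4% (n = 30) or 2.7% (n = 24); two-sided 4.9% or 5.4%.
- GEE arm-by-week-13 term: 2.2% to 3.7% favourable; 5.1% to 7.0% two-sided.

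**The case against.** The strongest reply is that the analysis paragraph must be read as a whole. It opens with a directional comparison of TOLF with e-Lymph, and the decision sentence itself ends in a comparative conclusion. The control arm has its own indicator in the model. Standard software given an intercept and both indicators would drop one column, and with e-Lymph as reference the coefficient for the intervention group is the difference wanted. On that view the sentence is clumsy and nothing more. The trial is also a pilot, concerned first with feasibility and acceptability.

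Much of this stands. The comparative intent is plausible, and under it there is no inflation. What does not follow is that the text can be left alone. No reference arm or contrast is named anywhere, one indicator per arm fits the arm-specific reading at least as well, and pilot or not, the plan commits to a formal conclusion at alpha 0.05.

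Three stronger inferences are tempting, and the documents do not support them:
- *That no reading yields a between-arm test, or that the control certainly plays no part.* The reference-coded reading yields one.
- *That a significantly worse TOLF result would also count as success.* Sidedness is unstated, but the hypothesis and the conclusion are both directional.
- *That the logit model would call a 22% TOLF rate a success in about 90% of trials.* The arithmetic is right for a no-intercept, single-visit test against 50% with n = 30. But essentially all of those rejections are rates significantly below 50%, which the directional hypothesis would not count as better.

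**Conclusion.** The concern holds as a mismatch between hypothesis and decision rule. It does not establish that the authors intended a within-arm test. If the rule is applied within the TOLF arm, the chance of a false claim of superiority with equal arms is 36% to 99% at 30 per arm and 29% to 96% at 24 per arm, over assumed common improvements of 0.3 to 0.8 SD of change. For complete pain reduction it is 67% and 44%, if the earlier trial's control rate of 22% applies to both arms. If the rule is applied as a reference-coded difference, this problem disappears.

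The continuous-outcome figures rest wholly on the assumed improvements, because the plan gives neither an SD nor an expected change. As this is the only efficacy rule in the plan, its meaning should be settled before the analysis. Whether one or all primary outcomes must be significant is a separate question.

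**What to change.** **Model.** For continuous outcomes, replace the two indicators with a single arm indicator (e-Lymph as reference) plus visit and arm-by-visit terms. Alternatively, model the post-baseline visits adjusted for the baseline value, keeping the visit and arm-by-visit terms so that week 13 can be read off. For complete pain reduction, model the post-baseline visits only, since no woman can have the outcome at baseline.

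A single arm indicator alone is not enough. Fitted to weeks 0, 9 and 13, it averages in the pre-randomisation visit. With balanced data and an equal effect D at weeks 9 and 13, it estimates (0 + D + D)/3 = two-thirds of D, and it does not target the week 13 endpoint.

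**Decision rule.** Replace the sentence with:

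> TOLF is concluded better than e-Lymph on an outcome only if the estimated TOLF minus e-Lymph contrast at week 13 (odds ratio for complete pain reduction) favours TOLF with two-sided p<0.05, reported with its 95% CI; within-arm changes are descriptive.

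**Cost.** A few sentences of analysis text. There are no new data, visits or participants, and if the comparative reading was intended all along, the intended comparison is unchanged.

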2.0 PROTECTION OF HUMAN SUBJECTS

We will obtain human subject approval and necessary HIPAA waivers from the Internal Review Board (IRB). We will obtain written informed consent from all participants. We will fully disclose all risks and benefits to the participants and give them ample opportunity to decline participation. Documentation is provided here and for each of the Human Subjects' points.

2.1. Human Subjects Involvement and Characteristics

This two-phase project uses qualitative (i.e., focus group) and pilot randomized clinical trial (RCT) design to adapt behavioral interventions (The-Optimal-Lymph-Flow [TOLF]) to be culturally appropriate, and subsequently test the interventions in Black and Hispanic patients. Thus, participants in this work are Black and Hispanic women (over age 18) with lymphatic pain following breast cancer treatment. These women will be recruited for the **Phase I focus groups** (N=24), and the **Phase II RCT** (N=60).

2.2. Recruitment and Informed Consent

All recruitment procedures will comply with HIPAA guidelines. The recruitment procedure will be as follows. For potential participants from University Health, potential participants will be identified through electronic medical record review, or their medical team or potential participants will call the researchers if they see the study flyer and are interested in the study. Once a potential participant has been identified, their primary oncologists will be contacted for permission to attempt to recruit the participant for this study if the potential participants are from University Health. If the oncologist agrees, potential participants will be told about the study by a member of the medical staff and asked if they would be willing to talk with a member of the study team. Potential participants will also be sent an email or a letter through postal mail letting them know that someone will call about the study or meet them at their clinic visit or give them a number to call to completely opt out of any further study activities. If interested in participating in the study, an appointment will be scheduled at which time the study will be explained in detail and signed consent will be obtained.

For potential participants from communities, potential participants will call or email the researchers to express their interest in the study and the researchers will contact the potential participants to confirm their interest in the study and eligibility.

Once a potential subject confirmed their interest in the study either from University Health or communities, a member of the study team will meet the potential participants either in person or virtual as they prefer, the researcher will describe the study in detail, provide the patient with consent forms either in paper or electric form, and offer to answer any questions about the study. Potential participants will then be given sufficient time to read over the consent form, at which time the PI or a member of the study team will ask if they have any further questions. The final component of the consent process will involve reviewing a brief checklist that outlines the major aspects of the study to confirm that the subject fully understands the protocol.

Research subjects will also be asked to carefully review the section in the consent form, entitled, PERMISSION (AUTHORIZATION) TO USE OR SHARE HEALTH INFORMATION THAT IDENTIFIES

YOU FOR A RESEARCH STUDY, at the time they sign the general study consent form. This document, written to ensure compliance with HIPAA Privacy Rule guidelines, provides detailed information about what information is being collected, the participant's privacy rights, and to whom the information may be disclosed. The participant will then sign the consent either in-person or through the electronic signature and be given a signed copy of the consent forms for their records.

Each participant in the focus group will be assigned a pseudonym (i.e., a fake name) to safeguard her identity and protect privacy. The focus group session will be audio recorded using a digital recorder. The audio-recording(s) will be used to transcribe only using pseudonym and ensure the accuracy of each woman's experience from the focus group discussions. Only the research team will have access to the audio recording. For focus group conducted in zoom and in person, pseudonyms will be used throughout the whole session.

For pilot RCT, each participant will be assigned a unique study ID (e.g., TOLF_001 to TOLF_060).

2.3. Protection Against Risk.

The primary risks of this study are those associated with confidentiality. There is some risk attendant to confidentiality of self-report data. Two password protected databases will be used for this study to ensure confidentiality. First, a tracking database will be used for recruitment and follow-up. This data will house information related to tracking the participants in the study, such as phone numbers and addresses. No medically sensitive or outcome data will be stored in this database. This database will also track nonparticipants (i.e., those who have declined participation) only to the barest minimum to ensure that they are not contacted again about participation. At the end of the study, all identifiable data of non-participants such as their names will be deleted. Tracking data on participants will be retained for the usual required period. Second, all study data will be stored in a separate password protected database without any personal identifiers. Data in this database will be derived from patients' direct input into the electronic patient reported outcomes system which is an online survey system; data entered into this system is stored on a secure server housed behind the UMKC firewall. Only a unique study identification number will link the electronic data to the study data file. The tracking data and study data will be stored in a file on a secure study computer which can only be accessed by necessary members of the research team. Access to the computer requires a password protected.

2.4. WOMEN AND MINORITY INCLUSION IN CLINICAL RESEARCH

Inclusion of Women: Sex as a Variable: Breast cancer occurs predominantly in women (13%; 1-in-8 women lifetime risk) than men (0.1%).¹ Each year, an estimated 268,600 women in the US are diagnosed with invasive breast cancer but only about 2,670 men.¹ As such, 100% of patient participants will be women.

Inclusion of Minorities: This proposed project aims to develop culturally appropriate, highly accessible, and effective behavioral interventions to reduce lymphatic pain and prevent lymphedema that will address barriers related to social determinants of health faced by Black and Hispanic women. Thus, the project includes only Black and Hispanic women with lymphatic pain following breast cancer treatment.

Inclusion of Individuals Across the Lifespan: Breast cancer does not occur in prepubescent children.¹ Breast cancer rarely occurs in individuals under age 18, individual under age 18 who are diagnosed with invasive breast cancer will be excluded. The project includes only adult women over age 18 with pain and swelling following breast cancer treatment.

